8.4.2 Safety variables and other evolution variables

The safety variables and other evolution variables (recruited at different times) will be the follow:

- Adverse Events evaluations for the primary outcomes:
 - Rate of AEs
 - Rate of SAEs
 - Rate of AEs (CTCAE) ≥ 3 excluding palmar-plantar erythrodysthesia
 - Rate of related-AEs
 - Rate of AEs leading to treatment discontinuation
 - Rate of death
- Variables related to the secondary outcomes:
 - Objective Response Rate (ORR)
 - Rate of patients who develop new extrahepatic spread
 - Overall survival (OS)
 - Time to progression (TTP)
 - Pattern of progression.
 - Intrahepatic growth (IHG).
 - New intrahepatic lesion (NIH)
 - Extrahepatic growth (EHG)
 - New extrahepatic lesion (NEH): emergence of new extrahepatic lesions or emergence of vascular invasion
 - Post-progression survival (PPS)
- BCLC staging system and CHILD-PUGH scale
- Tumor disease assessment
- Central test and stool test
- Tumor biopsy
- Physical examination
- General examinations: vital signs, ECOG and oxygen saturation

- Laboratory test:
 - Urinalysis
 - Hematology
 - Biochemistry and electrolyte
 - Thyroid function
 - Specific laboratory test
- EQ-5D
- FACT-Hep
- EORTC-QLQ-C30
- EORTC QLQ-HCC18
- Exitus information
- Survival status by follow-up
- Cabozantinib treatment information
- Visit control (conducted yes/no)
- Screen failure information
- End of treatment
- End of study
- Concomitant medication
- The rest of Adverse Events evaluations
- Protocol deviations

8.5 STUDY ESTIMAND, HANDLING OF MISSING DATA AND CENSORING RULES

The handling of missing data will follow the principles specified in the ICH-E9 and the CPMP/EWP/1776/99 Rev1¹³. Guideline on Missing Data in confirmatory trials Guidelines. As per the ICH E9(R1) (Addendum on estimands and sensitivity analysis in clinical trials EMA/CHMP/ICH/436221/2017)¹⁴, the plan for the assessment of the Primary endpoint (PEP) (in this study includes the main secondary outcome) is described here after using the 4 attributes of the estimand:

1. Population: as described in protocol and section 8.1 of this SAP, all analyses will be carried out using Safety population.
2. Endpoints: (please see details on the endpoints definitions in section 8.3)
 - a. Non confirmatory primary endpoints (PEPs): the rate and type of:
 - Any AEs
 - Related-AEs
 - Rate of death
 - AEs leading to treatment discontinuation
 - Serious AEs (SAEs)
 - Rate of AEs (CTCAE)≥3 excluding palmar-plantar erythrodysthesia
 - b. Secondary endpoints (SEP):
 - ORR (main secondary outcome)
 - Overall survival (OS)
 - Time to progression (TTP)

- Pattern of progression
- Post-progression survival (PPS)
- Rate of patients who develop new extra-hepatic spread

3. **Intercurrent events (ICEs)**: the relevant intercurrent events expected to occur in this study includes the following situations and the method for handling will be the same for all of them due to the safety characteristics of the primary objective. The “Treatment Policy” strategy will be used, i.e., all observed data will be used regardless of the intercurrent event.

- a. No treatment initiation: exclusion from the analysis.
- b. Main estimand: any other situation regardless of the ICE (use of rescue medication, prohibited concomitant medication, treatment discontinuation, or any reason leading to study discontinuation): “Treatment Policy” strategy (i.e. all observed data will be considered regardless of any previous ICE).
- c. Supplementary estimand: for some relevant efficacy secondary endpoints, data after ICEs will be censored (see table below) and will be based on the while on treatment strategy.

4. **Population-level summary**:

- a. Estimation of rates and 95%CI for the PEPs by means of Clopper-Pearson exact method will be used as the population-level summary (see sections 8.6.5.1 and 8.6.5.2.1).
- b. Time to event variables will be described using the Kaplan-Meier method (see section 8.6.5.2.2).

	Primary Estimand	Supplementary Estimand
Primary endpoints		
Any AEs Related-AEs Rate of death AEs leading to treatment discontinuation Serious AEs (SAEs) Rate of AEs (CTCAE)≥3 excluding palmar-plantar erythrodysthesia	Treatment policy	None
Secondary endpoints		
ORR (main secondary outcome)	Treatment policy	While on treatment*
Overall survival (OS)		
Time to progression (TTP)		
Pattern of progression	Treatment policy	None
Rate of patients who develop new extra-hepatic spread		
Post-progression survival (PPS)		

*(censored after treatment ICEs)

The ORR rate will be handled using the Treatment Policy strategy. In the unexpected case of missing due to no radiologic assessment was conducted, the composite strategy will be applied by imputing to ORR to failure.

No formal imputations will be performed for any other variable. For the categorical variables the analyses will be based on the Available Data Only (ADO) approach. With regards to the continuous variables, mixed models^{15,16,17} are robust to the presence of missing at random (MAR) and conducts the analysis with all participants despite the presence of missingness. Of note, this method calculates the estimations based on the variance-covariance structure but without any formal imputations.

No formal imputation will be used for dates due to all post-inclusion dates are complete date.

8.5.1 Censoring rules

TPP:

- Death without progression will be censored at the time of the last adequate radiological tumor assessment.
- Progression documented between scheduled assessments: Event at date of adequate radiological tumor assessment
- If a patient has not progressed at the time of database cutoff, the TPP of this patient will be censored at the last adequate tumor assessment before the database cutoff.
- Documented progression or death after missing ≥ 2 consecutive post-baseline tumor assessments: date of last adequate tumor assessment before missed assessments or date of inclusion, whichever is later.
- Patient lost to follow-up (or withdrew consent from study participation) before documented progression: date of last adequate tumor assessment.
- Please see comment below on the “treatment policy” and “while on treatment” estimands

Overall survival (OS):

- If a patient is alive at the time of last contact before the database cutoff, the OS of this patient will be censored at the date of last contact.
- Patient lost to follow-up (or withdrew consent from study participation) before death: date of last documented alive information
- Please see comment below on the “treatment policy” and “while on treatment” estimands

Post-progression survival (PPS)

- Same rules as OS

Handling of “treatment policy” and “while on treatment” estimands: If a patient discontinues study treatment or any other ICE is recorded before any event is documented, data from this patient will not be censored for the primary estimand (treatment policy). However, data will be censored for the supplementary estimand (while on treatment) at the last tumor assessment before the discontinuation of study treatment.

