Follow-up will include clinical and laboratory assessment every 2 weeks within the first 2 month, then every 4 weeks, tumor evaluation at week 4 and every 8 weeks thereafter. In addition, unscheduled visits will be made should they be needed (adverse events or symptoms). At each time point that the dose is changed we will perform a blood extraction to determine serum biomarkers. Moreover, a second extraction will be done 7 days after modifying the cabozantinib dose. Adverse events will be graded following version 5.0 of the CTCAE of the National Cancer Institute, during treatment and 30 days after the last dose. Tumor evaluation during follow-up will be evaluated by CT-scan. Response and TP will be defined according to the RECIST criteria v1.1. Outcomes will be measured from the date of starting cabozantinib until the date of death regardless of cause of death. TTP will be defined as the time from the starting date of cabozantinib to disease progression (according to RECISTv1.1). PPS will be measured from the date of detecting progression at radiology until the date of death or

last follow-up. Assessment will be done by radiologists in each center and then a central revision by radiologists with more than 10 years of experience in HCC and blinded to the evolution and outcome of the patients. Disease-control rate (DCR) will be defined as the percentage of patients who had a best-response rating of complete response (CR), partial response (PR) or stable disease (SD) (according to RECIST and BCLC-RECIST) maintained for at least 28 days after the first demonstration of best-response rating as per independent radiologic review.

Statistical & Analytical Plan and Methodology

The study will be analyzed using standard statistical methods to estimate rates and 95%CI (for ORR and other binary variables) by means of the Clopper-Pearson exact method, and the Kaplan-Meier method to describe the survival functions and the median and [95%CI]. A Statistical Analysis Plan, which will include all details regarding all analyses, the interim method, the handling of missing data and any plan for the analysis, will be finalized before the initiation of the study recruitment.

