1.2.4.1 TREATMENT SCHEDULE

Cabozantinib will be initiated at full dose (60 mg/day) and this dose will be modified upon development of adverse events according to the manufacturer's recommendations. Cabozantinib will be continued at the dose that the patient can tolerate. Treatment will continue until symptomatic tumor progression, unacceptable adverse events, patient decision or death.

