4.1.4 DISCONTINUATION OF CABOZANTINIB

Subjects MUST discontinue study medication:

- Withdrawal of informed consent (subject's decision to withdraw for any reason)
- Any clinical AE, abnormal laboratory test results or any illness which, in the opinion of the investigator, indicates that continued participation in the study is not in the best interest of the subject.
- Clinical deterioration ([Section 6.1.7](#))
- Pregnancy
- Termination of the study by the promoter
- Specific criteria for discontinuation of outlined in ([Section 6.1.6](#))
- Loss of ability to freely provide consent through imprisonment or involuntary incarceration for treatment of either a psychiatric or physical (eg, infectious disease) illness.
- Protocol defined disease progression unless subject is eligible for treatment beyond progression ([Section 6.1.7.1](#)).
- In the case of pregnancy, the investigator must immediately notify the Medical Monitor/designee of this event. In most cases, the study drug will be permanently discontinued in an appropriate manner. If the investigator determines a possible favorable benefit/risk ratio that warrants continuation of study drug, a discussion between the investigator and the Principal Investigator must occur.
- All subjects who discontinue should comply with protocol specified follow-up procedures as outlined in section. The only exception to this requirement is when a subject withdraws consent for all study procedures or loses the ability to consent freely (ie, is imprisoned or involuntarily incarcerated for the treatment of either a psychiatric or physical illness). If a subject was withdrawn before completing the study, the reason for withdrawal must be entered on the appropriate CRF page.

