6.1.7 STOPPING RULES FOR CLINICAL DETERIORATION

Clinical deterioration will be assessed to have occurred after a clinical event that, in the Investigator's opinion, is attributable to disease progression, is unlikely to reverse with continued study treatment and

therefore indicates that the subject is not benefiting from study treatment and cannot be managed by the addition of supportive care (such as bisphosphonates, bone directed radiotherapy, thoracentesis or paracentesis of accumulating effusions). The decision to continue or stop treatment should be discussed with the Principal Investigator and Medical Monitor as well as will be documented in the study files.

Examples of events that may, in the Investigator's opinion, indicate a lack of clinical benefit include, but are not limited to, the following:

- Performance status decrease of at least 2 points from baseline despite transitory cabozantinib interruption for at least 4 weeks
- Skeletal related events defined by spinal cord or nerve root compression.
- Development of new central nervous system metastases or Grade 3 encephalopathy despite transitory cabozantinib interruption for at least 2 weeks
- Any setting where the initiation of new anti-neoplastic therapy has been deemed beneficial to the patient.

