The duration of overall response is measured from the time measurement criteria are first met for CR/PR (whichever is first recorded) until the first date that recurrent or progressive disease is objectively documented (taking as reference for progressive disease the smallest measurements recorded on study).

The duration of overall complete response is measured from the time measurement criteria are first met for CR until the first date that recurrent disease is objectively documented.

Stable disease duration

Stable disease is measured from the start of the treatment until the criteria for progression are met, taking as reference the smallest sum on study (if the baseline sum is the smallest, this is the reference for calculation of PD).

Table 8 Response for patients with target and non-target lesions

| Target Lesions | Non-Target Lesions | New Lesions | Overall Response | Best Response for this category also requires |
|-------------------|-----------------------------|-------------|------------------|---|
| CR | CR | No | CR | |
| CR | Non-CR/Non-PD | No | PR | |
| CR | Not evaluated | No | PR | |
| PR | Non-PD or not all evaluated | No | PR | |
| SD | Non-PD or not all evaluated | No | SD | documented after 8 wks. |
| Not all evaluated | Non-PD | no | NE | |
| PD | Any | Yes or No | PD | |
| Any | PD | Yes or No | PD | |
| Any | Any | Yes | PD | |

Subjects with a global deterioration of health status requiring discontinuation of treatment without objective evidence of disease progression at that time should be reported as "symptomatic deterioration". Every effort should be made to document the objective progression even after discontinuation of treatment.

Table 9: Response for patients with non-target lesions only

| Non-Target Lesions | New Lesions | Overall Response |
|--------------------|-------------|------------------|
| CR | No | CR |
| Non-CR/Non-PD | No | Non-CR/non-PD* |
| Not evaluated | No | NE |
| Unequivocal PD | Yes or No | PD |
| Any | Yes | PD |

** Non-CR/non-PD is preferred over "stable disease" for non-target disease.*

Methods of Measurement

The cytological confirmation of the neoplastic origin of any effusion that appears or worsens during treatment when the measurable tumor has met criteria for response or stable disease is mandatory to differentiate between response or stable disease (an effusion may be a side effect of the treatment) and progressive disease.

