7.2.1 Cabozantinib

Cabozantinib will be initiated at full dose (60 mg/day) and the dose will be modified upon development of adverse events according to the manufacturer's recommendations and continued until symptomatic tumor progression, unacceptable adverse events, patient decision or death.

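### SAP 8.5.1 has no TTP rule for patients who stop for symptomatic progression without a timely later scan; by default they are censored at their last scan, which can bias TTP upward

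*SAP*

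**What the plan says.** **Event.** The protocol synopsis (Follow-up period) states: "TTP will be defined as the time from the starting date of cabozantinib to disease progression (according to RECISTv1.1"). Clinical progression without imaging is not an event.

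**Reasons to stop.** Protocol 1.2.4.1 says: "Treatment will continue until symptomatic tumor progression, unacceptable adverse events, patient decision or death". SAP 7.2.1 repeats this. Protocol 6.1.7 adds clinical deterioration, an event that in the investigator's opinion "is attributable to disease progression, is unlikely to reverse with continued study treatment". Protocol 4.1.4 also lists "Protocol defined disease progression unless subject is eligible for treatment beyond progression".

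**Recording.** Protocol Appendix 3 (14.3) covers "Subjects with a global deterioration of health status requiring discontinuation of treatment without objective evidence of disease progression at that time". It has them reported as symptomatic deterioration and asks for every effort to document objective progression afterwards. Protocol 6.1.6 asks for protocol evaluations to continue after withdrawal from treatment. Footnote 2 of Table 5 makes imaging after end of treatment preferred rather than required, and only if no other treatment starts. The schedule marks no tumour assessment at the end-of-treatment visit.

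**Censoring.** SAP 8.5.1 has TTP bullets for death without progression, progression between scheduled scans, no progression at cutoff ("the TPP of this patient will be censored at the last adequate tumor assessment before the database cutoff"), progression or death after two or more missed scans, and loss to follow-up or withdrawal. A closing paragraph says that a treatment stop does not censor under the primary treatment-policy estimand. Under the supplementary while-on-treatment estimand it censors at the last scan before the stop. Symptomatic deterioration is not mentioned.

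**The concern.** Kaplan-Meier assumes that a censored patient has the same future risk of progression as the patients still followed. A patient taken off cabozantinib because the investigator judged that the disease had progressed, and not scanned afterwards, is censored because of progression. The curve then looks better the more often progression is recognised clinically.

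Neither planned TTP estimand bounds this. The primary one counts such patients only if a timely scan follows. The supplementary one censors every patient who stopped before RECIST progression, so it leans the same way. The protocol synopsis lists progression-free survival, but SAP 8.3.2 does not carry it forward, so TTP is the SAP's only time-to-event measure of progression. Post-progression survival (PPS) starts at radiological progression and leaves these patients out.

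Protocol 9.1 foresees indirect comparison of the study's confidence intervals with external data. A shifted TTP estimate therefore matters somewhat, even though nothing is tested.

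**Working it through.** The documents give no expected TTP, event count or power, so there is no plan figure to reproduce. The check has two parts.

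**1. Path of a patient with symptomatic deterioration and no earlier RECIST progression**

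| What happens next | Primary estimand | While-on-treatment |
|---|---|---|
| Timely scan shows RECIST progression | Event at that scan | Censored at last scan before stop |
| Progression documented after two or more missed scans | Censored before the gap | Censored at last scan before stop |
| Death, no further scan | Censored at last scan (or before the gap) | Censored at last scan before stop |
| Lost to follow-up or consent withdrawn | Censored at last scan | Censored at last scan before stop |
| Alive at cutoff, no further scan | Censored at last scan | Censored at last scan before stop |

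Only the first row yields an event, and only in the primary estimand.

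**2. Size at 26 weeks**

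Inputs:
- True median TTP of 5.2 months. This is an assumption, borrowed from the phase 3 PFS figure in Protocol 1.2.3. 5.2 months = 22.6 weeks, so the weekly hazard is ln 2 / 22.6 = 0.0307, taken as constant.
- Scans at week 4 and every 8 weeks thereafter (protocol synopsis; Table 5 agrees). The last scan before week 26 is week 20, so three intervals count: 4, 8 and 8 weeks.
- f, the share of progressions that are symptomatic and never scanned. The documents do not give it; 10%, 20% and 30% are assumed.
- Standard error 0.082 at n=40, from simulated trials. The binomial approximation √(0.542 × 0.458 / 40) = 0.079 agrees.

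The probability of progressing within an interval is q = 1 − exp(−0.0307 × length): 0.115 for 4 weeks and 0.217 for 8 weeks.

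Reference, with every progression dated at the next scheduled scan: S = (1 − 0.115)(1 − 0.217)² = 0.542.

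Under SAP 8.5.1 a share f of each interval's progressors is censored at the preceding scan and leaves the next risk set. Of those at risk, 1 − fq remain and (1 − f)q have events, so each factor becomes 1 − (1 − f)q / (1 − fq) = (1 − q) / (1 − fq). Hence S(f) = 0.542 / [(1 − 0.115f)(1 − 0.217f)²].

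| f | Denominator | S(f) | Shift (points) | Shift / 0.082 |
|---|---|---|---|---|
| 0 | 1 | 0.542 | 0 | 0 |
| 10% | 0.946 | 0.573 | 3.1 | 0.4 |
| 20% | 0.894 | 0.606 | 6.4 | 0.8 |
| 30% | 0.844 | 0.642 | 10.0 | 1.2 |

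If half of these patients are scanned at the next visit, f is halved: the shifts become 1.5, 3.1 and 4.7 points, about 0.2, 0.4 and 0.6 SE.

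A large simulation on the same scan grid, read at week 28, gives 0.46, 0.50 and 0.54 against 0.42 with full capture. The direction and order of size are the same. In that simulation the median, which can only fall on a scan date, stays at 6.4 months for f up to 20% and moves to 8.3 months only at 30%.

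**The case against.** The case for leaving the SAP alone has several parts.

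- **These patients are not without rules.** Appendix 3 names the category and asks for objective documentation after the stop; Protocol 6.1.6 asks for evaluations to continue. A reader might infer that no rule of any kind exists. That goes too far: what is missing is the TTP rule.
- **Stopping for symptoms does not censor in the main analysis.** A reader might infer that it does. SAP 8.5.1 says otherwise for treatment policy; only the absence of a timely later scan leads to censoring.
- **Some patients will already have an event.** RECIST progression is itself a reason to stop, and Protocol 6.1.7.1 allows treatment beyond it. A patient with radiological progression who later stops for symptoms has both a TTP event and a PPS start date.
- **RECIST-only TTP is a defined endpoint.** The protocol also starts PPS at radiological detection, so leaving these patients out of PPS follows from the definition. An investigator-judged event in an open-label, single-arm trial carries its own bias.
- **The data will be visible.** End-of-treatment reasons, tumour assessments and subsequent treatments are tabulated or listed (SAP sections 9 and 10).
- **Little depends on it.** SAP 8.6 calls the analysis non-inferential, ORR is ranked first among the secondary outcomes, and OS captures these patients in full.

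All of this stands as a limit on the point. It does not remove it. The instructions to image later are best-effort, imaging is only preferred and lapses when new therapy starts, and progression found after two missed scans is set aside. Listings let a reader find these patients but do not show what they do to the curve.

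**Conclusion.** The point holds in a limited form. SAP 8.5.1 leaves a gap for symptomatic deterioration without a timely later scan. The default is informative censoring at the last adequate scan, and its direction is upward.

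The size is conditional: about 3, 6 or 10 points at 26 weeks for never-scanned shares of 10%, 20% or 30%, about half that if half are scanned later, and zero if the share is zero. This rests on an assumed 5.2-month median, a constant hazard, the week-4-then-8-weekly grid, and the same share in every interval.

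Three stronger readings are tempting and not supported. That TTP *is* biased upward cannot be said without knowing the share. That these patients are too ill to be scanned again is not in the documents; Protocol 6.1.7 speaks of lack of benefit, not of ability to undergo imaging. Larger shifts of about 4, 8 and 13 points appear if symptomatic events are dated when they occur while radiological events wait for the next scan (progression estimates 0.469 against 0.429, 0.474 against 0.391, 0.483 against 0.356), but part of that is a difference in dating, not censoring bias.

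No document figure is wrong, and no test, sample size or primary conclusion changes. This is a cheap improvement.

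**What to change.** Keep RECIST-only TTP under treatment policy as the main analysis. In SAP 8.5.1:

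1. State the default explicitly: a patient recorded as symptomatic deterioration with no timely later scan showing RECIST progression is censored at the last adequate scan.
2. Add one TTP sensitivity analysis in which stopping cabozantinib for symptomatic progression or clinical deterioration (Protocol 6.1.7), without prior RECIST progression, is an event on the date of that decision.
3. Report the number of such patients beside the main TTP result, and how many were scanned later.
4. Leave PPS defined from radiological progression, with a note that it excludes these patients. Any repeat that includes them is supplementary.

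The cost is SAP wording, one count and one extra Kaplan-Meier run. End-of-treatment data are already planned for Table 44 and Listing 31, and Protocol 6.1.6 already requires the decision date when treatment is withdrawn for lost clinical benefit. Treatment and scan schedules do not change.

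There are two cautions. The added event is investigator-judged in an open-label trial, so it should stay a sensitivity analysis. Because it is dated at the decision and not at the next scan, its gap from the main curve will somewhat overstate the censoring bias. If few such patients occur, the analysis will show that TTP is robust.

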7.3.2 Discontinuation of cabozantinib

Subjects MUST discontinue study medication:

- Withdrawal of informed consent (subject's decision to withdraw for any reason)
- Any clinical AE, abnormal laboratory test results or any illness which, in the opinion of the investigator, indicates that continued participation in the study is not in the best interest of the subject.
- Clinical deterioration (see protocol section 6.1.7 for more details)
- Pregnancy
- Termination of the study by the promoter
- Specific criteria for discontinuation of outlined in (see protocol section 6.1.6 for more details)
- Loss of ability to freely provide consent through imprisonment or involuntary incarceration for treatment of either a psychiatric or physical (eg, infectious disease) illness.
- Protocol defined disease progression unless subject is eligible for treatment beyond progression (see protocol section 6.1.7.1 for more details).
- In the case of pregnancy, the investigator must immediately notify the Medical Monitor/designee of this event. In most cases, the study drug will be permanently discontinued in an appropriate manner. If the investigator determines a possible favorable benefit/risk ratio that warrants continuation of study drug, a discussion between the investigator and the Principal Investigator must occur.
- All subjects who discontinue should comply with protocol specified follow-up procedures as outlined in section. The only exception to this requirement is when a subject withdraws

consent for all study procedures or loses the ability to consent freely (ie, is imprisoned or involuntarily incarcerated for the treatment of either a psychiatric or physical illness). If a subject was withdrawn before completing the study, the reason for withdrawal must be entered on the appropriate CRF page.

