7.3.3 Post study drug study follow-up

In this study, overall survival is a secondary endpoint. Subjects who discontinue study drug must continue to be followed for collection of survival follow-up data until death or the conclusion of the study. Survival follow-up visits should be planned every 3 months from Follow-Up Visit-1 and may be performed by phone contact or office visit.

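### The supplementary while-on-treatment analysis of OS censors at the last scan before cabozantinib is stopped, so it discards observed deaths informatively and does not estimate OS

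*SAP*

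**What the plan says.** SAP 8.5 sets treatment policy as the main estimand and adds a supplementary one: "for some relevant efficacy secondary endpoints, data after ICEs will be censored (see table below"). In the table that follows, ORR, OS and TTP appear to share one while-on-treatment cell, footnoted "censored after treatment ICEs". Pattern of progression, new extrahepatic spread and PPS fall in a block with no supplementary estimand.

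SAP 8.5.1 confirms that OS is included. Its OS list carries the pointer beginning "Please see comment below on the", which leads to the closing paragraph on the two estimands. For the primary estimand, "data from this patient will not be censored for the primary estimand (treatment policy"). For the supplementary one: "However, data will be censored for the supplementary estimand (while on treatment) at the last tumor assessment before the discontinuation of study treatment". PPS is told to follow the OS rules.

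On stopping, SAP 7.2.1 says treatment is "continued until symptomatic tumor progression, unacceptable adverse events, patient decision or death". SAP 7.3.2 lists among the mandatory reasons "Clinical deterioration (see protocol section 6.1.7 for more details"). On follow-up, SAP 7.3.3 says: "Subjects who discontinue study drug must continue to be followed for collection of survival follow-up data until death or the conclusion of the study".

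OS is summarised by Kaplan-Meier with a median and 95% CI (SAP 8.6.5.2.2). SAP 8.6 declares the analyses non-inferential.

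**The concern.** Kaplan-Meier treats a censored patient as having the same future risk of death as those still under observation. Here patients are censored because they stop drug, and they stop largely because they are deteriorating, progressing with symptoms or not tolerating treatment. Those who remain are selected for doing well. The deaths that follow stopping are not missing: the trial goes on collecting them, and the rule removes them.

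Two further defects are matters of definition. A tumour assessment date has no meaning as an OS censoring date, because the patient is known to be alive after it. A patient who stops before the first on-study scan has only the baseline scan to be censored at, that is, at time zero or earlier.

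At stake is a supplementary OS median and interval that could be read as survival. Protocol 9.1 plans indirect comparisons with external data through the 95% CIs of the study estimates, and SAP Table 11 and Figure 1 are titled only as overall survival, with no estimand label.

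**Working it through.** The documents give no event count or projection for this analysis, so there is no figure of theirs to reproduce.

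**Inputs from the documents**
- True median OS 10.2 months, from the phase 3 cabozantinib arm (Protocol 1.2.3), used as an anchor.
- Median PFS 5.2 months (same place), used as a proxy for median time on drug, *m*. This is an assumption; 3.5 and 7 months are also shown.
- Scans at week 4, then every 8 weeks (Protocol synopsis, follow-up period).
- N = 40. Enrolment March 2020 to July 2022 and patients complete in October 2023, so follow-up is 15 to 43 months, taken as uniform.

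**Input not in the documents**
- *q*, the share of treatment exits that are deaths on drug. Range shown: 10% to 50%.

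**Model.** Exit from treatment has constant hazard λ = ln 2 / *m*. The death hazard on drug is *q*λ. After stopping for another reason, death has constant hazard *h*, solved so that median OS is 10.2 months:

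S(t) = exp(−λt) + [(1−q)λ / (h−λ)] × [exp(−λt) − exp(−ht)]

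**Censoring at discontinuation** leaves only on-drug deaths, so Kaplan-Meier estimates exp(−qλt), with median *m*/*q*.

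Example, *m* = 5.2 and *q* = 0.20: λ = 0.6931/5.2 = 0.1333 per month; *q*λ = 0.0267; *h* = 0.161, six times the on-drug hazard. Apparent 12-month OS = exp(−0.0267 × 12) = 73%, and the apparent median is 5.2/0.20 = 26.0 months. True 12-month OS from the formula is 42%.

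**The SAP rule** moves each censoring date back to the preceding scan. I simulated this with 400,000 patients per scenario, three times.

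Results for *m* = 5.2 months:

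| q | True 12-month OS | Censored at stopping: 12-month OS, median | SAP rule: 12-month OS, median | Deaths kept, of those observed (per 40 patients) | Deaths removed |
|---|---|---|---|---|---|
| 10% | 42% | 85%, 52.0 | 84%, not reached | 3.9 of 36.4 | 89% |
| 20% | 42% | 73%, 26.0 | 70%, 23.3 to 23.7 | 7.7 of 36.1 | 79% |
| 30% | 43% | 62%, 17.3 | 59%, 16.0 | 11.6 of 35.7 | 68% |
| 40% | 43% | 53%, 13.0 | 50%, 12.1 | 15.4 of 35.0 | 56% |
| 50% | 44% | 45%, 10.4 | 43%, 9.8 | 19.3 of 33.8 | 43% |

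**Other times on drug, SAP rule**
- *m* = 3.5: medians of about 30, 15.2, 10.4 and 8 months for *q* = 10% to 40%. At 30% the 12-month OS is 45% against a true 44%; at 40% it is 35% against 45%.
- *m* = 7: medians not reached, 32.7, 21.9, 16.6 and 13.4 months for *q* = 10% to 50%.

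**Where the bias vanishes.** On-drug and off-drug death hazards are equal when *q*λ = ln 2 / 10.2, that is, *q* = *m*/10.2: 0.34, 0.51 and 0.69 for *m* = 3.5, 5.2 and 7. Below that share, censoring at stopping overstates OS; above it, it understates OS.

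**Patients with no on-study scan before stopping.** Week 4 is 28/30.44 = 0.92 months, so the share is (1−q)(1 − exp(−0.92λ)). For *q* = 10% to 50% this runs from 15.0% to 8.3% (*m* = 3.5), 10.4% to 5.8% (*m* = 5.2) and 7.8% to 4.4% (*m* = 7), or about 4% to 15% overall.

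**The case against.** A reader might infer that the rule removes most deaths and grossly inflates survival. The documents do not support that as a general statement. Both parts depend on *q*, which they do not give. At 5.2 months on drug and 50%, a minority of deaths is removed and the median is slightly below the truth; at 3.5 months and 40%, the bias runs the other way. PFS is also an imperfect proxy for time on drug, because Protocol 6.1.7.1 allows treatment beyond radiological progression; some later deaths would then occur on drug and stay as events. These points stand, and they limit the claim to a curve that can substantially overstate OS.

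It is also tempting to blame the scan date for the inflation. The table shows the opposite: backdating lowers the curve a little (about 23.5 against 26.0 months at *q* = 20%), because it removes time at risk and keeps the on-drug deaths. The inflation comes from censoring at discontinuation.

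Nor is the trial's main OS result biased. Primary OS keeps deaths after stopping, no decision rests on the supplementary figure, and neither document says that it would be the one compared with external data. With about four deaths left, readers would see a median that is not reached on very few events.

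What survives is the matter of principle. The SAP's own stopping reasons tie discontinuation to prognosis, so equal hazards on and off drug would be a coincidence. Even then, the rule throws away deaths the trial has recorded.

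**Conclusion.** The concern holds as a defect in one supplementary, descriptive analysis. The while-on-treatment rule reaches OS through both the SAP 8.5 table and the OS list in SAP 8.5.1, its censoring is informative by the plan's own stopping reasons, and the resulting Kaplan-Meier curve does not estimate OS.

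The size is conditional. With 5.2 months on drug and a true median of 10.2 months, the excess in apparent 12-month OS runs from about 42 percentage points (*q* = 10%) to none (*q* = 50%). It is larger with 7 months on drug and reverses at *q* = 40% with 3.5 months. These figures rest on constant hazards, on external medians taken as anchors and on an assumed *q*; they show a range and are not a forecast.

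Two points do not depend on *q*: a scan date is not a meaningful OS censoring date, and the instruction that PPS follows the OS rules conflicts with the table, which gives PPS no supplementary estimand.

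**What to change.** - Remove OS from the while-on-treatment cell of the SAP 8.5 table. In SAP 8.5.1, delete the OS pointer to the closing paragraph and exclude OS from that paragraph's supplementary rule. Treatment policy then stands as the only OS estimand.
- State that PPS is also outside the while-on-treatment rule, which reconciles 8.5.1 with the table.
- If an on-treatment mortality summary is wanted, report deaths on treatment or within 30 days of the last dose. These are already collected (Protocol 7.2.1), and AEs with outcome of death are already tabulated (SAP 8.6.5.3.7). Give them as a count, or as a cumulative incidence with discontinuation as a competing event.

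The cost is SAP wording and the loss of one supplementary analysis. No data collection changes and the primary OS analysis is untouched.
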